ABG provides an effective osteoconductive scaffold for new bone formation and contains appropriate growth factors and cells to potentiate new bone formation (osteoinductive). The availability of locally-harvested bone in ankle or foot arthrodesis can be limited, therefore, a second harvest site is often required from either the iliac crest, proximal or distal tibia to facilitate the acquisition of enough bone to support the graft substitute application. Harvesting ABG, however, is associated with both short- and long-term morbidity. Complications of autograft harvest include blood loss, postoperative pain, fracture, infection, other non-infectious wound complications, heterotopic bone formation, hernia, and nerve injury. Baumhauer and colleagues recently

reported the results of a prospective randomized study of patients undergoing ankle and hindfoot fusion procedures using ABG harvested from one of four sites (iliac crest, proximal tibia, distal tibia, and calcaneus). Clinically significant pain at the bone graft harvest site was reported by 35% of patients 3 weeks postoperatively and 18% had persistent pain up to 1 year. A review of the literature suggests that the overall complication rate from tibial graft sites, although it has become a favored source for autograft material for foot and ankle surgery, is 5.5%. These complications range in severity from hematoma/seroma and paresthesia to infection, fracture and invasion of the joint space.

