### 6.1.5 Post-Operative Care

While in the hospital, subjects should be encouraged to mobilize out of bed by the first post-operative day. Physical therapy for ambulation and activities of daily living should also be provided per standard of care. The following will be performed prior to subject's release from the hospital or within 1 week following the procedure:

- Collect A/P, lateral and oblique X-rays of the hindfoot/ankle after implant

Hospital discharge will occur in accordance with the institutions' standard of care. Discharge instructions will include prescriptions for pain management. Sites should provide standard-of-care prophylaxis for thromboembolic disease and this may include ASA up to 325 mg bid. With the exception of ASA up to 325 mg bid for either cardiovascular protection and/or DVT prophylaxis, subjects will be instructed to avoid non-steroidal anti-inflammatory drugs (NSAIDs) and corticosteroids for the first 6 weeks following surgery. Subjects will be advised that the use of NSAIDs or systemic steroid therapy (not including topical steroid therapy) may interfere with bone healing. This also applies to limited use of NSAIDs for headache, dysmenorrhea, etc. Electromagnetic, ultrasound or osteobiologic treatments stimulating bone growth are not allowed. Subjects will be instructed to remain non weight-bearing for six (6) weeks, then allowed to progressively increase weight-bearing. During the progressively increased weight-bearing timeframe, a removable cast/splint or boot is worn, which is subsequently weaned after full weight-bearing is achieved. It is recommended that all subjects are directed to participate in a post-operative rehabilitation program consistent with the guidelines provided in [Table 2](#). Subjects will be advised against the use of tobacco products for at least six (6) months after surgery. Tobacco products will be defined as all tobacco products (cigarettes [including e-cigarettes], cigars, and chewing tobacco) and will include gum or patches that contain nicotine. Subjects will be advised that nicotine may increase the chances of wound infection, pseudarthrosis (nonunion) and other complications.

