### 9.9 Handling of Missing Data

For the primary and key secondary analyses, the imputation method of LOCF will be used in subjects with an unknown outcome.

Sensitivity analyses of missing data will be performed by utilizing the following imputation methods:

- 1) “missing-equals-failure”
- 2) multiple imputation methods

- 3) a tipping point analysis will be performed for the primary and key secondary efficacy endpoints which will allow assessment of sensitivity without need for postulating any missing data mechanism. For this analysis, all possible combinations of missing data from the two arms will be considered, and the point at which significance is no longer achieved will be identified.

The planned sensitivity analyses for the primary and key secondary endpoints will be described in further detail in the Statistical Analysis Plan (SAP).

All data collected on safety or adverse events will be reported to the extent it is available, regardless of the active/withdrawn status of participants.

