9.2 Primary Endpoint

9.2.1 Primary Variable Analysis

The primary efficacy endpoint will be the proportion of subjects who meet all of the following criteria for the SPC at 52 weeks:

- Improvement in pain on weight-bearing at fusion site (≥ 20 mm reduction from baseline on 100 mm VAS)
- Absence of significant graft harvest site pain (< 20 mm on 100 mm VAS)
- Improvement in Foot and Ankle Ability Measure Activities of Daily Living subscale (FAAM-ADL) (≥ 8 points improvement from baseline)
- Absence of device related or procedure related SAEs (up to Week 52)
- Absence of secondary surgical or nonsurgical interventions intended to promote fusion (up to Week 52)

The primary analysis will assess a non-inferiority of AMPLEX to ABG, and it will be claimed if the lower bound of the 2-sided 90% CI for the difference of the proportions (AMPLEX minus ABG) is greater than -12.0%. The superiority will be claimed if the lower limit of the 2-sided 95% CI is greater than zero. The CI will be constructed with the normal approximation to the binomial. In addition, the response status for each component will be summarized.

A subject will be considered an SPC success if he/she meets all of the SPC criteria, otherwise, the subject will be considered an SPC failure. The SPC response status will be determined for 12, 24, and 52 weeks. The response status for the visit-based components (i.e., weight-bearing pain, graft harvest site pain, and FAAM-ADL) will be assessed for each time point based on the windowed analysis visits. The response status for the non-visit-based components (i.e., absence of device or procedure related SAEs and secondary interventions to promote fusion) will be assessed in a period up to the actual visit date that the corresponding visit-based variables for a particular analysis visit are collected. If the actual visit dates among the visit-based variables are different at the analysis visit, the latest visit date among them will be used to determine the period for the assessment of the non-visit-based variables. If any of the components of the SPC at an analysis visit is missing, the SPC response status will be considered missing for the analysis visit. Note that the graft harvest site pain will be collected only for the ABG group, and therefore, no data for this component will be recorded for the AMPLEX group.

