For the primary analysis, the last available SPC response status will be used (i.e., the last observation carried forward; LOCF) if the SPC response status at 52 weeks is missing. If no SPC response status data are available at previous visits, the SPC response status at 52 weeks will be considered failure.

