9.3 Secondary Endpoint(s)

9.3.1 Key Secondary Endpoint

The key secondary efficacy endpoint will be the proportion of subjects who meet the following criteria for the CT radiographic fusion success at 52 weeks:

- Radiographic evidence of fusion by CT scan ($\geq 50\%$ bone bridging across the joint space for the full complement of joints in the absence of secondary surgical or nonsurgical interventions intended to promote fusion)

Non-inferiority of AMPLEX to ABG will be claimed if the lower bound of the 2-sided 90% CI for the difference of the proportions (AMPLEX minus ABG) is greater than -12.0%. The superiority will be claimed if the lower limit of the 2-sided 95% CI is greater than zero. The CI will be constructed with the normal approximation to the binomial.

A subject will be considered a CT radiographic fusion success if he/she has $\geq 50\%$ bone bridging across the joint space by the CT scan for all treated joints without secondary surgical or nonsurgical interventions intended to promote fusion, otherwise, the subject will be considered a CT radiographic fusion failure. The CT radiographic fusion response status will be determined for 12, 24, and 52 weeks. The response status will be assessed for each time point based on the windowed analysis visits. The response status for the absence of secondary interventions to promote fusion will be assessed in a period up to the actual visit date that the corresponding CT images for a particular analysis visit were collected. If any of the components of the CT radiographic fusion success criteria at an analysis visit is missing, the response status will be considered missing for the analysis visit.

For the key secondary analysis, the last available CT radiographic fusion response status will be used (i.e., the last observation carried forward; LOCF) if the response status at 52 weeks is missing. If no CT radiographic response status data are available at previous visits, the response status at 52 weeks will be considered failure.

The same set of sensitivity analyses as for the primary endpoint will be conducted for the key secondary endpoint. These sensitivity analyses will be conducted regardless of the testing results of the primary efficacy endpoint. Therefore, no multiplicity among sensitivity analyses will be adjusted.

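### The primary and CT analyses fill a missing Week-52 outcome with Week-12 or Week-24 status, when the protocol itself describes outcomes as still changing, so the one-sided 5% error rate is not assured

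*SAP*

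**What the plan says.** SAP 9.2.1 gives its primary rule in these words: "last available SPC response status will be used (i.e., the last observation carried forward; LOCF) if the SPC response status at 52 weeks is missing". It adds: "If no SPC response status data are available at previous visits, the SPC response status at 52 weeks will be considered failure". SAP 9.3.1 does the same for the key secondary endpoint, where "the last available CT radiographic fusion response status will be used". Protocol 9.6.2 has the rule for the SPC, and Protocol 9.9 covers both endpoints: "For the primary and key secondary analyses, the imputation method of LOCF will be used in subjects with an unknown outcome".

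The carried value has two possible sources before Week 52: "The SPC response status will be determined for 12, 24, and 52 weeks". LOCF is triggered easily, because one missing component is enough: "If any of the components of the SPC at an analysis visit is missing, the SPC response status will be considered missing for the analysis".

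On the course of recovery, Protocol 6.1.5 says: "Subjects will be instructed to remain non weight-bearing for six (6) weeks, then allowed to progressively increase weight-bearing". Protocol Table 2 has patients in a boot or brace from Week 6 to Week 12 and in physical therapy from Week 12 to Week 24. Protocol 7.2.1.2 sets bridging at zero after surgery and follows its progression. On harvest-site pain, Protocol 1.1 cites clinically significant pain "reported by 35% of patients 3 weeks postoperatively and 18% had persistent pain up to 1 year". SAP 9.2.1 records this component in the ABG arm only.

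SAP 9.2.2 plans missing-equals-failure, multiple imputation and tipping-point analyses as sensitivity analyses. Protocol 3.4.1 rests study success on SPC non-inferiority in the mITT set. Neither document gives a reason for choosing LOCF.

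**The concern.** LOCF is a fair stand-in for Week 52 only if a subject's status at Week 12 or 24 is what it would be at Week 52. The protocol describes a population for whom that is not expected.

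Two mechanisms could matter in a non-inferiority test. If success rates are lower in both arms mid-recovery, and the arm difference is proportionally smaller too, mixing in early values shrinks a true deficit. Separately, if harvest-site pain is still resolving, an early value counts ABG failures that would have cleared by Week 52, with no counterpart in AMPLEX.

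At stake is the error rate of the single test that decides the trial, and of the CT test that follows it in the fixed sequence.

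**Working it through.** **1. Reproduce the design.** Inputs from SAP 3.2: 62% AMPLEX, 60% ABG, margin -12 points, one-sided 5%, 264 and 132 subjects. SE = sqrt(0.62×0.38/264 + 0.60×0.40/132) = 0.0521. Power = Φ(0.14/0.0521 - 1.645) = 85.2%, matching the stated 85% with 396 subjects.

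**2. Baseline at the margin.** Take ABG 60%, AMPLEX 48%, 320 and 160 subjects. SE = sqrt(0.48×0.52/320 + 0.60×0.40/160) = 0.0477. The chance of claiming non-inferiority is Φ(0 - 1.645) = 5.0%.

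**3. Effect of LOCF.** With a share m missing, each arm's expected rate is (1-m) × Week-52 rate + m × carried rate, and P(claim) = Φ((d + 0.12)/SE - 1.645). With equal m, the expected difference is (1-m)×(-12) + m × (carried difference). LOCF therefore favours the claim only when the carried difference is less negative than -12 points.

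Assumptions for the central case:
- ABG harvest pain is 18% at Week 52 (the cited 1-year figure), and components are independent, as in the plan's own sample-size reasoning. ABG success on the shared components is then 0.60/0.82 = 73.2%.
- At the carried visit, shared components are at 70% of their Week-52 level in both arms, and harvest pain is 25%.
- Every subject with a missing Week-52 status has an earlier status, and would have had the same Week-52 rate as the rest of the arm.

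Carried rates: AMPLEX 0.48×0.70 = 33.6%; ABG 0.732×0.70×0.75 = 38.4%; difference -4.8 points.

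| Missing, both arms | AMPLEX | ABG | Expected difference | One-sided error |
|---|---|---|---|---|
| 5% | 47.3% | 58.9% | -11.6 | 5.8% |
| 10% | 46.6% | 57.8% | -11.3 | 6.7% |
| 15% | 45.8% | 56.8% | -10.9 | 7.8% |

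For the last row: 0.85×0.48 + 0.15×0.336 = 0.4584; 0.85×0.60 + 0.15×0.3841 = 0.5676; Φ(0.0108/0.0481 - 1.645) = 7.8%.

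**4. The two mechanisms apart, at 15% missing.** Harvest pain alone (25%, no general recovery effect): -11.2 points, 6.9%. General recovery alone (70%, pain held at 18%): -11.5 points, 6.3%.

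**5. Upper limit with equal missingness.** Carried harvest pain of 35%, 15% missing and no general recovery effect give -10.1 points and 10.5%.

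**6. Reversal.** Keep the central case at 15% missing, but let AMPLEX recover more slowly than ABG's 70%:
- AMPLEX factor 0.55: carried 26.4%, arm rates 44.8% and 56.8%, difference -12.0, error 5.0%.
- AMPLEX factor 0.50: carried 24.0%, arm rates 44.4% and 56.8%, difference -12.4, error 4.3%.

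Unequal missingness, with both arms back at 70%:
- AMPLEX 20%, ABG 5%: 45.1% and 58.9%, difference -13.8, error 2.2%.
- AMPLEX 10%, ABG 25%: 46.6% and 54.6%, difference -8.0, error 20.5%.

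**7. CT fusion.** ABG 70% (lower end of Protocol 9.1), AMPLEX 58%, 15% missing. Early bridging success at 70% of its Week-52 level multiplies both rates by 0.85 + 0.15×0.70 = 0.955: 55.4% and 66.9%, difference -11.5, error 6.3%. At 50% the multiplier is 0.925: 53.7% and 64.8%, difference -11.1, error 7.3%.

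**8. Missing-equals-failure.** At 15% missing the difference is 0.85×(-12) = -10.2 points, with error 10.2%. This analysis shrinks a true deficit as well.

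**The case against.** The strongest objection is that the direction is not established. The documents give no Week-12 or Week-24 rates by arm and no missingness by arm. A reader might infer that LOCF necessarily favours AMPLEX; steps 3 and 6 show that it does so only under assumptions that the documents neither state nor exclude. This stands.

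A reader might also take about 10% as the realistic error rate. It needs carried harvest pain of 35%, which is the cited 3-week figure. SPC status does not exist at 3 weeks, and the SAP's Week-12 window opens on Day 65. The protocol also does not say that clinically significant pain in the cited study means this trial's 20 mm cut-off. About 10% is therefore an extreme limit for equal missingness.

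The 15% may be too high for Week 52. Protocol 9.1 gives no time point, but SAP 3.2 ties it to 78-week completers, and the Week-52 window (Day 268 to 456) rescues late visits. Some carried Week-24 values will also fall at or after the end of the rehabilitation programme, since that window runs to Day 267. Both points reduce the size of the effect; the mismatch remains.

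Finally, sensitivity analyses are planned. Multiple imputation and the tipping-point grid could expose a problem, but they do not decide success, and missing-equals-failure may agree with LOCF for the wrong reason.

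**Conclusion.** The concern holds as a weakness in the primary missing-data rule, not as a demonstrated bias in one direction. LOCF assumes stability where the protocol describes change, and no justification is offered, so the stated one-sided 5% depends on recovery speed and dropout by arm, which are unknown. Under equal missingness and proportional recovery, with the assumed 70% and 25%, error at a true -12 points is about 5.8% to 7.8% for 5% to 15% missing. For CT at 15% missing it is about 6-7%, through the general-recovery mechanism alone, since harvest pain plays no part there. The inflation is modest in these cases and can vanish or reverse if AMPLEX recovers more slowly or has more missing data. The change is worth making because the better method is already written into the SAP.

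**What to change.** In SAP 9.2.1 and 9.3.1 and Protocol 9.6.2 and 9.9:
- Make the component-level multiple imputation of SAP 9.2.2 (treatment, baseline and preceding visits as predictors; 100 imputations; Rubin's rules) the primary handling of missing Week-52 SPC and CT status.
- Score any observed component failure as a failure. As written, a Week-24 success with a later related SAE or fusion-promoting intervention and a missing Week-52 VAS could be carried forward as a success.
- Name the imputation predictors before database lock; the SAP now says only baseline characteristics.
- Move LOCF to the sensitivity list, keep the tipping-point analysis, and do not cite missing-equals-failure as protection against a false non-inferiority claim.

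The cost is a slightly wider confidence interval, reliance on a missing-at-random model, the work of specifying that model, and a protocol amendment. No new data or visits are needed. The gain from multiple imputation was not simulated here; it depends on the model being adequate, which is why the tipping-point analysis should stay.

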9.2.2 Sensitivity Analysis

The following sensitivity analyses will be conducted to assess the robustness of the primary analysis:

- As-treated analysis based on actually received treatment on the mITT analysis set
- Analysis on the ITT analysis set
- Analysis on the PP analysis set

The same analysis conducted for the primary analysis will be repeated for these sensitivity analyses.

In addition, sensitivity analyses using the following approaches for the handling of missing data will be conducted:

- Missing-equals-failure approach
- Multiple imputation
- Tipping point analysis

Missing-equals-failure approach:

All subjects with missing SPC status at 52 weeks will be considered failures.

Multiple imputation methods:

The missing data for each component of the SPC for 12, 24, and 52 weeks will be imputed sequentially by regression-based imputation models using treatment group, baseline characteristics, and outcomes from preceding visits as predictors. The missing SPC response status will be calculated based on the imputed data. This imputation procedure will be repeated 100 times, and the primary analysis method will be applied to each of the imputed datasets. A combined estimate of the difference of the proportions (AMPLEX minus ABG) and the corresponding two-sided 90% CI will be obtained by the methods described in Rubin (1987) (3).

Tipping point analyses:

Let n_{1m} and n_{2m} be the number of subjects with missing SPC response status at 52 weeks in AMPLEX and ABG group, respectively. The tipping point analysis will assess the non-inferiority in all possible combinations of missing data imputation (i.e., $(n_{1m}+1)*(n_{2m}+1)$ imputations), and the result will be presented graphically. Specifically, the horizontal and vertical axes of the graph will be the number of subjects imputed as success in AMPLEX group (i.e., ranges between 0 and n_{1m}) and the number of subjects imputed as success in ABG group (i.e., ranges between 0 and n_{2m}), respectively. The non-inferiority outcome (i.e., supportive or not supportive) will be plotted for each combination of the number of successes from each group in the graph by different symbols (e.g., a solid circle for supportive and an open circle for not supportive outcomes). Note that each result with the LOCF method (i.e., primary analysis) and with the missing-equals-failure approach will be represented as one of the combinations in the graph.

The primary endpoint will also be analyzed for the following subgroups for the mITT analysis set, and the treatment group difference of the proportions of subjects with SPC success for each subgroup will be presented in forest plots.

- Demographic characteristics: age, gender, and race
- Baseline comorbidities: obesity, diabetes, previous ankle/hindfoot surgery, smoking history, primary etiology
- Surgical site: affected side, fusion site (single, double, triple, or ankle)
- Investigational site
- Geographical region (US or non-US)

The treatment group comparisons after controlling each factor listed above will be conducted by stratified analyses using the Mantel Haenszel method as sensitivity analyses.

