9.1 General Considerations

Non-inferiority tests will be conducted at a one-sided 5% significance level whereas superiority tests will be conducted at a two-sided 5% significance level per an agreement with the FDA in the AMPLEX IDE.

All efficacy analyses will be conducted for the mITT analysis set unless specified otherwise. The primary and key secondary efficacy endpoints will be analyzed by a fixed-sequence procedure according to the following order to maintain the overall Type 1 error rate to a one-sided 5% for non-inferiority and a two-sided 5% for superiority testing.

- 1) Non-inferiority of AMPLEX to ABG in the primary efficacy endpoint (primary analysis)
- 2) Non-inferiority of AMPLEX to ABG in the key secondary efficacy endpoint
- 3) Superiority of AMPLEX to ABG in the key secondary efficacy endpoint
- 4) Superiority of AMPLEX to ABG in the primary efficacy endpoint

Testing procedure will begin with the non-inferiority test for the primary efficacy endpoint, and each test will be conducted without adjustment of multiplicity as long as all preceding tests are significant. All other secondary endpoints will be presented with the point estimate of the treatment group difference and the corresponding 2-sided 90% and 95% confidence intervals.

For visit-based data, the data collected on the day that is closest to the scheduled trial day within a window specified in Table 1 will be assigned to the corresponding analysis visit. If the closest day cannot be uniquely identified for an analysis visit, the data collected on an earlier trial day will be assigned to the analysis visit. Visit windows for the analysis are specified in a way to utilize all collected data as much as possible and are different from the protocol specified visit windows.

Table 1 Scheduled trial day and window for analysis visits

Analysis visit	Scheduled trial day	Analysis window
Baseline	Day -84 to Day 1	Up to prior to the initiation of surgery
Post-Operative CT and X-ray	Day 1	Day 1 to Day 29
Week 2	Day 15	Day 2 to Day 29
Week 6	Day 43	Day 30 to Day 64
Week 12	Day 85	Day 65 to Day 127
Week 24	Day 169	Day 128 to Day 267
Week 52	Day 365	Day 268 to Day 456
Week 78	Day 547	Day 457 to Day 637

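### Missing-equals-failure keeps the -12% margin while shrinking the difference it tests, so with similar, largely outcome-unrelated loss in both arms it is an anti-conservative check of non-inferiority

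*SAP*

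**What the plan says.** SAP 9.2.1 sets the hypothesis and the rule. "The primary analysis will assess a non-inferiority of AMPLEX to ABG", and the claim is made if the "lower bound of the 2-sided 90% CI for the difference of the proportions (AMPLEX minus ABG) is greater than -12.0" per cent. On the interval it says: "The CI will be constructed with the normal approximation to the binomial". SAP 9.1 sets the level: "Non-inferiority tests will be conducted at a one-sided 5% significance level".

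The primary analysis fills a missing 52-week SPC status by LOCF, and by failure only where no earlier status exists (SAP 9.2.1).

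SAP 9.2.2 then opens its list with "The following sensitivity analyses will be conducted to assess the robustness of the primary analysis". Three of the analyses concern missing data: missing-equals-failure, multiple imputation and a tipping-point analysis. The first is defined in one sentence: "All subjects with missing SPC status at 52 weeks will be considered failures". It applies to both arms and carries no margin of its own. The tipping-point graph confirms which rule applies, because missing-equals-failure is one of its cells and each cell is marked as supporting non-inferiority or not.

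Protocol 9.9 names the same three methods ("Sensitivity analyses of missing data will be performed by utilizing the following imputation methods"). SAP 9.3.1 extends them to CT fusion: "The same set of sensitivity analyses as for the primary endpoint will be conducted for the key secondary endpoint".

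**The concern.** Counting missing subjects as failures is a familiar cautious choice when the aim is to show superiority, because it pulls the two arms together. In a non-inferiority test, pulling the arms together is what helps the claim. If both arms lose a similar fraction for reasons largely unrelated to outcome, the filled-in difference is smaller than the true difference, yet it is still compared with -12%.

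What is at stake is the weight a reader gives to agreement. If the primary result passes and missing-equals-failure passes too, that will look like independent support. Under the stated conditions the check is tilted towards passing, and the tilt grows with the amount of missing data. The same holds for CT fusion.

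**Working it through.** **Inputs.** ABG 60%, AMPLEX 62%, margin -12 points, one-sided 5%, 264 + 132 evaluable, 320 + 160 randomized, about 15% discontinuation (SAP 3.2, Protocol 9.1). The decision rule is the lower limit of the unpooled normal-approximation 90% interval (SAP 9.2.1). The planned numbers imply the same loss in both arms: 264/320 = 132/160 = 82.5% retained, so 17.5% lost.

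**The plan's own figure reproduces.** SE = sqrt(0.60×0.40/132 + 0.62×0.38/264) = 0.0521. Power = Φ((0.02 + 0.12)/0.0521 − 1.645) = Φ(1.04) = 85.2%, against the stated 85% with 396 subjects.

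**Dilution.** Let m be the fraction missing in each arm, unrelated to outcome. Missing-equals-failure replaces each rate p by p(1 − m), so the tested difference is (1 − m) times the true one. At m = 0.15 and true rates of 48% vs 60%:

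- AMPLEX 0.48 × 0.85 = 40.8%; ABG 0.60 × 0.85 = 51.0%; difference −10.2 points.
- SE = sqrt(0.408×0.592/320 + 0.510×0.490/160) = 0.0481.
- Pass probability = Φ((−0.102 + 0.12)/0.0481 − 1.645) = Φ(−1.27) = 10.2%. Exact binomial enumeration gives 10.3%.
- A filled-in difference of −12 points corresponds to a true deficit of 0.12/0.85 = 14.1 points.

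**Pass rate at a true −12 points, 320 vs 160, exact enumeration, equal loss unrelated to outcome:**

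| Missing in each arm | SPC (48% vs 60%) | CT fusion (60.5% vs 72.5%) |
|---|---|---|
| 0% | 4.9% | 4.7% |
| 5% | 6.1% | 6.2% |
| 10% | 7.9% | 8.1% |
| 15% | 10.3% | 10.3% |
| 17.5% | 11.7% | 11.4% |

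The CT control rate is the midpoint of the 70% to 75% assumed in Protocol 9.1. Analysing only observed subjects at 15% loss (272 vs 136) gives 5.1% for SPC. Varying the ABG rate from 50% to 80% at 15% missing leaves the SPC figure between 10.0% and 10.5%.

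**Unequal loss (SPC):**

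| AMPLEX missing | ABG missing | Tested difference | Pass rate |
|---|---|---|---|
| 17% | 11% | −13.6 points | 2.5% |
| 16% | 13% | −11.9 points | 5.3% |
| 15% | 16% | −9.6 points | 12.8% |
| 14% | 17% | −8.5 points | 18.1% |

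**Loss related to outcome (15% missing in each arm).** If missing subjects succeed at half the overall rate, the pass rate is 6.9%. If all of them are true failures there is no dilution, and it is 4.9%.

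**At the design alternative (62% vs 60%, 15% missing).** Missing-equals-failure passes 88% of the time, against 86% for observed subjects alone.

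**The case against.** Four points can be made for the plan, and most of each stands.

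- **Other checks exist.** Where loss is unrelated to outcome, a correctly specified multiple imputation targets the true difference and holds about 5%. The tipping-point grid covers every combination, including all missing AMPLEX subjects failing and all missing ABG subjects succeeding. This limits the harm. It does not remove it: the SAP gives no criterion for which cells of the grid are plausible, and the only two cells it names are LOCF and missing-equals-failure.
- **No trial decision rests on this analysis.** Protocol 3.4.1 ties success to the primary analysis. A reader might infer from 10.3% that the trial's type I error is doubled. The documents do not support that, since the primary rule is LOCF and is untouched. With complete true data standing in for the primary analysis, at a true −12 points and 15% missing, missing-equals-failure agreed with 78% of false primary passes, against 67% for observed subjects alone. That gap is the false reassurance, and it is well short of a doubling.
- **The plan does not oversell it.** A reader might take missing-equals-failure as the plan's stringent or worst-case analysis. Neither document describes it so; it is one of three approaches.
- **The conditions may not hold.** SAP 3.2 ties its 15% to 78-week completers and the week-52 analysis window is wide (Day 268 to Day 456), so missingness at week 52 may be lower. A subject with a related SAE who then drops out is already a known failure, and coding that subject as one is right. In the other direction, any missing component makes SPC missing, and harvest-site pain is collected only in ABG (SAP 9.2.1), which gives ABG one more way to be missing.

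**Conclusion.** The concern holds with conditions. When loss is similar in both arms and largely unrelated to outcome, missing-equals-failure with the -12% margin is anti-conservative for non-inferiority, for SPC and for CT fusion. At a true −12 points it passes 6.1% to 11.7% of the time for SPC as missingness runs from 5% to 17.5%, against a nominal 5%.

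A flat statement that the check passes twice as often as it should goes too far. That figure needs about 15% missing at week 52, equal by arm and unrelated to outcome; at 10% missing the ratio is about 1.6 (7.9/5). About 3 points more loss on AMPLEX removes the inflation, and mostly failing dropouts shrink it. More loss on ABG enlarges it. This is a weakness in one of three missing-data sensitivity analyses, not in the primary test, and it is worth correcting because the correction is cheap.

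**What to change.** In SAP 9.2.2, and for CT fusion through 9.3.1:

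1. Keep missing-equals-failure as a descriptive result and for the superiority tests. State that it is not conservative for non-inferiority and does not count as evidence of robustness there.
2. Add one prespecified scenario under the non-inferiority null, at the level of the derived SPC (and CT fusion) status. Impute missing ABG subjects from the ABG model and missing AMPLEX subjects at a success probability 12 points below the ABG prediction. Combine with Rubin's rules, compare with -12%, and mark the scenario on the tipping-point graph.

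**Cost.** SAP wording and a separate binary imputation step, because the planned imputation works component by component and cannot simply be reused. No new data or subjects are needed, and the primary analysis is unchanged. The added check is stricter: at 62% vs 60% with 15% missing it passes about 79% of the time with Rubin's variance, against 88% for missing-equals-failure. At a true −12 points it passes 2.5% to 4.9% of the time, depending on the variance used.

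A simpler alternative is to multiply the margin for this one analysis by the retained fraction (0.12 × 0.85 = 0.102 at 15% missing). That brings the pass rate back to 5.1%, but only under equal loss unrelated to outcome.
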